**10/17/2022**

## **Study Protocol and Statistical Analysis Plan**

To reach people who had been in car accidents, an announcement was posted on social media, the research was detailed, and volunteers were asked to give their contact information using Google Forms. The volunteers were interviewed and were thoroughly informed about the study, the inclusion requirements were assessed, and a Google Form information comprising data collecting tools will be delivered to the participants who fulfilled the inclusion criteria.

The subjects will be randomly divided into groups and the EMDR 2.0 Group application and mhGAP will be applied to them online. Participants eligible for the applications were randomized to be 30 subjects (in three group). In both groups, the application will be made for three consecutive days. Those who will be unable to finish their applications at this stage will be ruled out of the study. Participants will be requested to complete out forms including data collection tools 1 week and 1 month after completing the applications. Following appropriate processing, the obtained data will be subjected to statistical analysis.

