### **Statistical Analysis**

SPSS 22 package program will be used to perform statistical analyses on study data. Descriptive data will be presented with frequency and percentage for categorical variables and mean and standard deviation for continuous variables. The Pearson Chi-square test for categorical variables and parametric assumptions for continuous variables will be used to compare the pre-application variables of the two groups, followed by the Student's T-test. The repeated measures analysis of variance will be used to see whether EMDR 2.0 Group Application and mhGAP procedures alone resulted in significant changes in the dependent variables and if there will be a difference in changes between the two groups. In cases where the Mauchly test revealed that the sphericity assumption will be violated, the Greenhouse-Geisser adjustment will be used, and the corrected results will be reported. The effect size will be determined using  $\eta^2$ . A value of  $p < 0.05$  will be considered statistically significant.

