#### **The Depression-Anxiety-Stress Scale-21**

The Depression-Anxiety-Stress Scale-21 (DASS-21) will be used in the study to determine the depression, anxiety, and stress symptoms of the participants. The scale has 21 items (Lovibond and Lovibond, 1995). Each question is evaluated on a four-point Likert-type scoring and it has seven items each for depression, anxiety, and stress. The score that can be obtained from the scale for each subdimension changes between 0 and 21. The Turkish validity and reliability study of the scale were conducted by Saricam (2018).

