#### **The Impact of Event Scale**

[figure not shown]
The Impact of Event Scale (IES-R) will be applied to measure the amount of effect of persons from an event in the study. It was developed by Weiss and Marmara in 1997 (Weiss, 2007). It is a self-report five-point Likert-type scale and includes 22 items. It evaluates the level of exposure to events in three different fields as "Intrusion," "Avoidance," and "Hyperarousal." The score that can be obtained from the scale varies between 0 and 88. The Turkish validity and reliability studies of the scale were carried out (Çorapçıoğlu et al., 2006).

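### Allocation is described only as random division and the comparison of changes is not adjusted for baseline, which costs precision in a small trial; add baseline adjustment, and stratify if allocation is still open

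*Combined protocol and SAP*

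**What the plan says.** All of the relevant design text is under the opening heading, Study Protocol and Statistical Analysis Plan.

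- **Allocation:** "The subjects will be randomly divided into groups". No stratification, blocking, allocation ratio, sequence generation or concealment is described anywhere.
- **Order of events:** before the randomisation text, the section says that "a Google Form information comprising data collecting tools will be delivered to the participants who fulfilled the inclusion criteria". The Statistical Analysis section then plans to "compare the pre-application variables of the two groups, followed by the Student's T-test". Baseline scores therefore appear to exist before allocation, although this is not stated outright.
- **Size:** "Participants eligible for the applications were randomized to be 30 subjects (in three group" is followed directly by "In both groups, the application will be made for three consecutive days". These two sentences do not agree on the number of arms, and it is unclear whether 30 is a total or a group size.
- **Exclusions:** "Those who will be unable to finish their applications at this stage will be ruled out of the study".
- **Scores:** for the IES-R, "The score that can be obtained from the scale varies between 0 and 88"; for the DASS-21, "The score that can be obtained from the scale for each subdimension changes between 0 and 21". No SD is given for either, and no primary outcome is named.
- **Outcome analysis:** repeated measures analysis of variance, asking whether change differs between the two groups. No baseline covariate is named.

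**The concern.** With about 15 people per arm, chance alone will often leave the arms visibly different on a symptom score at the start. The planned baseline tests report such a difference but do nothing about it. Comparing changes does not remove it either. With a baseline-to-follow-up correlation r, a baseline difference d moves the expected difference in change by (1 − r)d, so the arm that starts worse appears to improve more. At r = 0.5 and d = 0.5 SD the shift is 0.25 SD.

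At stake is how precise and how believable the between-arm result is. A reader who sees unequal arms at baseline cannot tell how much of an apparent advantage is regression to the mean. If the scores are already in hand, both the allocation and the model could use them at almost no cost.

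**Working it through.** The plan derives no sample size or power, so there is no figure of its own to reproduce.

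**Inputs.** From the plan: 30 randomised, two groups analysed, follow-up at 1 week and 1 month. Assumed: 1:1 allocation, normal scores with SD 1 at each visit, and r = 0.5 (range 0.4 to 0.6).

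**1. Chance of imbalance without stratification.** The SD of the baseline mean difference is √(1/n₁ + 1/n₂), and P(|d| ≥ 0.5) = 2[1 − Φ(0.5/SD)].

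| Reading of the 30 | SD of d | P(\|d\| ≥ 0.5 SD) |
|---|---|---|
| 15 v 15 | √(2/15) = 0.365 | 17.1% |
| 10 v 20 | √0.15 = 0.387 | 19.7% |
| 10 v 10 (any pair of three arms) | √0.2 = 0.447 | 26.4% |
| 30 v 30 | √(2/30) = 0.258 | 5.3% |

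With 12–13 per arm left after exclusions, the figure is 20–22%.

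**2. The same with stratification at the median (15 v 15).** For a normal score the variance within each half is 1 − 2/π = 0.363. The SD of d becomes √(0.363 × 2/15) = 0.220, and P(|d| ≥ 0.5) = 2.3%. Simulation of practical versions gives 2.6% to 4.2%, the highest being strata of 15 split 8/7.

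This applies only to the score used to stratify. For another score correlated ρ with it, the variance factor is 0.363ρ² + 1 − ρ²:
- ρ = 0.5: factor 0.841, SD 0.335, risk 13.5%.
- ρ = 0.8: factor 0.592, SD 0.281, risk 7.5%.

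**3. Error rate of the planned test.** In simulated null trials (15 v 15, plain random division, Greenhouse-Geisser arm-by-time test):
- Overall, at r = 0.5: about 4.7%.
- Given |d| ≥ 0.5 SD, with the two follow-ups correlated 0.7: 10.0%, 11.6% and 12.8% at r = 0.6, 0.5 and 0.4. With all correlations equal: 9.3–10.8%. The range is therefore about 9–13%.
- Otherwise, with all correlations 0.5: 3.7%, against 9.9% given the imbalance.

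The parts add up: 0.171 × 9.9% + 0.829 × 3.7% = 1.7% + 3.1% = 4.8%, in line with the overall 4.7%.

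**4. Variance of the between-arm contrast at one follow-up (15 v 15).**
- Change score: 2(1 − r) × 2/15 = 0.133 at r = 0.5.
- Follow-up adjusted for baseline: (1 − r²) × 2/15 × (1 + 1/26) = 0.104. The factor 1/26 is the cost of chance imbalance with 30 people. The reduction is 1 − 0.104/0.133 = 22%. The variance ratio is (1 + r)/2 × 27/26, so the reduction is 27% at r = 0.4 and 17% at r = 0.6.
- Change score with stratified allocation (simulated SD of d 0.247): (1 − r)² × 0.247² + (1 − r²) × 2/15 = 0.015 + 0.100 = 0.115, about 14% less than 0.133.
- Both together: about 0.101 in simulation, which is 2–3% below adjustment alone.

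Given |d| ≥ 0.5 SD, the baseline-adjusted test had an error rate of 4.5%. If allocation is stratified but the model contains neither the stratum nor the baseline score, the error rate falls to about 3%, so the test is conservative.

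**The case against.** The strongest reply is that nothing here is invalid. Plain randomisation keeps the planned test near its nominal 5%, and the 9–13% describes only the trials singled out for a large imbalance. A reader might infer that the plan produces biased results or a doubled error rate. The documents do not support that: averaged over allocations, the error is about 4.7%. This part of the reply stands in full.

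A reader might also take the brief wording to mean that allocation is unrestricted. The plan is silent on restriction, which is not a statement that there is none. Nor is 17% a property of this trial, because it needs a total of 30 in two equal arms, and the text can be read otherwise. The low figure after stratification does not describe severity in general, since it covers only the score used. Finally, that the scores precede allocation is inferred from narrative order, and the past tense in the sentence giving the number randomised may mean that allocation is finished.

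It is also fair to say that stratification is the lesser remedy. Baseline adjustment gives more (22% against 14%) and leaves stratification little to add. What survives is that the plan includes neither, and that adjustment is open to the sponsor whether or not allocation has happened.

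**Conclusion.** The point holds as a missed gain in precision and credibility. With 30 in total, two equal arms and a normal score, a baseline difference of 0.5 SD or more on any one score occurs in about 17% of allocations. The range runs from about 5% (30 per arm) to about 26% (any pair of three arms of 10). In the trials where this happens, the planned comparison of changes rejects falsely in about 9–13%, for r between 0.4 and 0.6 and depending also on the correlation between follow-ups. The larger omission is baseline adjustment in the Statistical Analysis section; the allocation sentence comes second. The size of the gain rests on r, which the documents do not give.

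**What to change.** 1. **Statistical Analysis section.** Compare the arms on the follow-up scores with the baseline value of the same score as a covariate, for the IES-R and each DASS-21 subscale. The cost is one sentence and one model term.
2. **Allocation, if not yet done.** Replace the random-division sentence with 1:1 allocation by computer-generated permuted blocks, stratified at the median baseline IES-R total, and state that the baseline forms are completed first. Carry the stratum in the between-arm model. The cost is a two-stratum list, a wait until the forms are returned, and a further model term. No extra participants or measurements are needed.
3. **Allocation, if already done.** Report the method actually used and rely on step 1.
4. **Sample size sentence.** Reconcile the number of groups, and state whether 30 is the total or the size of each arm and what the allocation ratio is. The imbalance figures should not be cited as facts about this trial until that is settled.

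### Randomised participants who do not finish the three-day course are removed before follow-up, so the arms are compared among completers only and the comparison is open to bias

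*Combined protocol and SAP*

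**What the plan says.** The section titled Study Protocol and Statistical Analysis Plan gives this sequence.

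- Data collection forms go out first: "a Google Form information comprising data collecting tools will be delivered to the participants who fulfilled the inclusion criteria".
- Allocation and delivery follow: "The subjects will be randomly divided into groups and the EMDR 2.0 Group application and mhGAP will be applied to them online". The course length is the same in each arm: "In both groups, the application will be made for three consecutive days".
- Non-finishers are then removed: "Those who will be unable to finish their applications at this stage will be ruled out of the study".
- Follow-up comes last: "Participants will be requested to complete out forms including data collection tools 1 week and 1 month after completing the applications".

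The Statistical Analysis section describes tests "used to compare the pre-application variables of the two groups" and a repeated measures ANOVA that is to show, among other things, "if there will be a difference in changes between the two groups". It names no analysis set, no method for missing data and no sensitivity analysis. The remaining sections only describe the questionnaires.

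**The concern.** The removal comes after randomisation and depends on something the assigned procedure can influence. The two arms receive different interventions, so the number who stop, and the kind of person who stops, may differ between them. If stopping is also related to how IES-R or DASS-21 scores would have changed, completers in one arm are no longer comparable with completers in the other, and the difference in change mixes the treatment effect with selection.

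Comparing pre-application variables does not settle this. Groups that match on measured baseline variables can still differ in prognosis or response. The result would also describe people who finished the course, not everyone randomised. And because follow-up is lost with the person, the trial could not find out afterwards how large the problem was.

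**Working it through.** **Reading the text.** The plan has no figure on this point to reproduce, so the first check is of the wording.

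1. Removal follows allocation and the three-day course, so it is a post-randomisation exclusion.
2. Non-finishers have no scheduled follow-up. The plan does not say so in those words; it follows from their removal and from follow-up dates that are defined only by completion.
3. Non-finishers should have baseline data, because the form goes to everyone meeting the inclusion criteria and pre-application variables are compared. This too is inferred; the text says the form is delivered, not when it is returned.
4. Nothing elsewhere brings these people back into the analysis.

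**Size, under assumed values.** The documents give neither a non-completion rate nor a gap between completers and non-completers, so every rate and gap below is an assumption. Let p be the share not completing in an arm, and d how much worse non-completers' change is than completers', in SDs of change. The completer mean exceeds the as-randomised mean by p × d, so

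bias in the arm difference = pE × dE − pM × dM (E = EMDR 2.0, M = mhGAP).

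The false-positive rate is P(|Z + bias/SE| > 1.96), with SE = √[1/(n(1−pE)) + 1/(n(1−pM))] for n randomised per arm (normal approximation). The number per arm is unclear: the plan gives 30 subjects and mentions three groups, but otherwise speaks of two. Hence n = 10, 15 and 30.

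| pE vs pM | d (both arms) | Bias (SD) | n=10 | n=15 | n=30 |
|---|---|---|---|---|---|
| 10% vs 5% | 0.5 | 0.05 × 0.5 = 0.025 | 5.0% | 5.0% | 5.1% |
| 10% vs 5% | 1.0 | 0.05 × 1.0 = 0.05 | 5.1% | 5.2% | 5.4% |
| 20% vs 5% | 0.5 | 0.15 × 0.5 = 0.075 | 5.3% | 5.4% | 5.8% |
| 20% vs 5% | 1.0 | 0.15 × 1.0 = 0.15 | 6.1% | 6.7% | 8.4% |
| 30% vs 10% | 0.5 | 0.20 × 0.5 = 0.10 | 5.4% | 5.7% | 6.4% |
| 30% vs 10% | 1.0 | 0.20 × 1.0 = 0.20 | 6.8% | 7.7% | 10.6% |

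Worked example, last row at n = 15: SE = √(1/10.5 + 1/13.5) = 0.411; bias/SE = 0.20/0.411 = 0.486; the two tails sum to about 7.7%.

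**When the bias is zero, and when it is not.** With d = 0, or with equal rates and the same d, it is zero. Equal rates alone are not enough: 15% in both arms with d = 1.0 in one and 0 in the other gives 0.15 × 1.0 − 0.15 × 0 = 0.15 SD, in either direction.

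**Scale.** Without losses, the standard error of the arm difference is √(2/n): 0.45 SD at 10 per arm, 0.37 at 15 and 0.26 at 30. Every bias above is below one standard error. A wider assumption, 40% versus 10% with d = 1.0, gives 0.40 − 0.10 = 0.30 SD and false-positive rates of 8.8%, 10.7% and 16.7% at 10, 15 and 30 per arm.

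**A separate, smaller gap.** The plan does not say what happens when someone who finished the course misses a follow-up form. Conventional repeated measures ANOVA drops anyone missing either form. If a share q misses each form, the loss lies between q and 2q, and is 1 − (1−q)² if the misses are independent: 10% to 20% (19%) for q = 10%, and 20% to 40% (36%) for q = 20%. The main point does not rest on this.

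**The case against.** The strongest reply is about size. No non-completion rate is given, the bias may be zero, and the illustrated values lie within one standard error. At 15 per arm, five of the six unequal-rate cases leave the false-positive rate at 6.7% or less. The course lasts only three days, is online and is taken by volunteers, so losses of 30% have no support in the documents. At 10 per arm the worst of the six cases reaches only 6.8%. All of this is correct, and it means that a bias is possible but not shown. It does not rescue the rule: the size cannot be known in advance, and following the rule ensures it cannot be learned later.

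A completer analysis is also legitimate in its own right, but as a supporting result. Here it is the only comparison the plan yields, with no justification and no planned report of non-completion by arm.

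Two narrower objections stand in part. The absence of follow-up for non-finishers is an inference, though a strong one. And missed forms among people who finished have a different cause and should not add weight to the main point.

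**Conclusion.** The concern holds and needs to be corrected. Followed exactly, the plan gives up the randomised comparison for one among completers. This is a fault in a stated rule, not a missing detail. The conclusion rests on the order of steps in the protocol and on the lack of any as-randomised analysis, not on the illustrated sizes. Those range from 0 to 0.20 SD in the main cases, with false-positive rates of about 5.0% to 7.7% at 15 per arm and up to 10.6% at 30 in the unequal-rate cases. They depend wholly on assumed rates and gaps, and the true direction is unknown.

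**What to change.** Replace the removal sentence with wording such as: *Participants who do not finish the applications remain in the study unless they withdraw consent, are sent the 1-week and 1-month forms timed from the scheduled last session day, and are analysed in the group to which they were randomised.*

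In the Statistical Analysis section:

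- Analyse all available data, including baseline, with a mixed model for repeated measures (SPSS MIXED, unstructured covariance). This also covers missed forms.
- Report non-completion by arm, with reasons and baseline scores.
- Keep the completer analysis as secondary.
- Add a delta-adjusted sensitivity analysis, because the mixed model assumes data are missing at random and a completer analysis does not test that. For example, set missing changes 0.5 and then 1.0 SD worse than the model predicts, in each arm separately and in both. That makes six scenarios per outcome and time point, so choose one outcome and one time point in advance.

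The first three items and the replaced sentence are essential; the details of the delta analysis are open to preference. The change affects data collection and analysis, not treatment.

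The cost is one protocol sentence, a different SPSS procedure, one table and the sensitivity analysis, which needs an imputation step or an equivalent adjustment beyond the mixed model. The forms are already online, so sending them adds little, but reminders take work and some non-finishers will not reply. If anyone has already been ruled out, late or missing forms must be reported. The estimated effect may move in either direction.

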### **Statistical Analysis**

SPSS 22 package program will be used to perform statistical analyses on study data. Descriptive data will be presented with frequency and percentage for categorical variables and mean and standard deviation for continuous variables. The Pearson Chi-square test for categorical variables and parametric assumptions for continuous variables will be used to compare the pre-application variables of the two groups, followed by the Student's T-test. The repeated measures analysis of variance will be used to see whether EMDR 2.0 Group Application and mhGAP procedures alone resulted in significant changes in the dependent variables and if there will be a difference in changes between the two groups. In cases where the Mauchly test revealed that the sphericity assumption will be violated, the Greenhouse-Geisser adjustment will be used, and the corrected results will be reported. The effect size will be determined using  $\eta^2$ . A value of  $p < 0.05$  will be considered statistically significant.

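### Change over time within an arm is to be read as the procedure's effect, although no untreated group is described; the planned between-group comparison should carry the inference

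*Combined protocol and SAP*

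**What the plan says.** The Statistical Analysis section gives the repeated measures ANOVA two jobs in one sentence. The first is "to see whether EMDR 2.0 Group Application and mhGAP procedures alone resulted in significant changes in the dependent variables". The second is to see "if there will be a difference in changes between the two groups". Neither is named as primary.

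The opening section, Study Protocol and Statistical Analysis Plan, describes the design:

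- **Arms:** "The subjects will be randomly divided into groups and the EMDR 2.0 Group application and mhGAP will be applied to them online". It adds: "In both groups, the application will be made for three consecutive days". No untreated, waiting-list or sham condition appears.
- **Numbers:** "Participants eligible for the applications were randomized to be 30 subjects (in three group)". The number of groups differs from the two groups used in the rest of the text.
- **Measurement:** before the applications, "a Google Form information comprising data collecting tools will be delivered to the participants who fulfilled the inclusion criteria". Forms are completed again 1 week and 1 month after the applications.
- **Non-finishers:** "Those who will be unable to finish their applications at this stage will be ruled out of the study".

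**The concern.** A time effect within one arm is a before-after comparison. It contains any effect of the procedure, but also recovery that would have happened anyway, regression to the mean among volunteers who met entry criteria, and the effect of answering the same questionnaires repeatedly. Randomisation removes none of these from a within-arm change. It makes them equal, in expectation, between arms, so only the comparison of arms is protected.

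The plan words the within-arm question causally and sets it beside the randomised comparison without ranking the two. If the aim is followed as written, a significant time effect in each arm could be reported as showing that both procedures work, even when the arms do not differ. These are people who have been in car accidents, so change without treatment is plausible. The documents state neither the time since the accident nor an entry score from which to judge how much to expect.

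**Working it through.** The plan gives no effect size, SD, correlation or sample-size calculation, so there is no figure of its own to reproduce. The logical point needs no numbers. The following shows what is at stake. Effect sizes, correlations, natural improvement and drop-out shares are all assumptions.

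**Arm size.** The text supports several readings: 30 subjects in two groups (30/2 = 15 per arm), 30 in three groups (30/3 = 10), or 30 in each group.

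**Within-arm test when the procedure does nothing.** Let natural improvement be d baseline SDs and the pre-post correlation r. The SD of change is √(2(1−r)), and the noncentrality of the paired t test is d√n / √(2(1−r)). For n = 15 and d = 0.3:

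- r = 0.5: 0.3 × 3.873 / 1.000 = 1.162, giving two-sided rejection probability 0.192.
- r = 0.7: 0.3 × 3.873 / 0.775 = 1.500, giving 0.287.

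Probability that a given arm is significant at 5% (r = 0.5 to r = 0.7):

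| Natural improvement | 10 per arm | 15 per arm | 30 per arm |
|---|---|---|---|
| none | 5% | 5% | 5% |
| 0.3 SD | 14–20% | 19–29% | 36–54% |
| 0.5 SD | 29–45% | 44–64% | 75–93% |

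**The planned three-visit ANOVA.** This was simulated with 4,000 runs per cell, r = 0.5, compound symmetry, and the same drift in both arms at both follow-ups. At 15 per arm the within-arm time test was significant in 18% of trials at 0.3 SD and 46% at 0.5 SD. The group-by-time test rejected in 4.0 to 5.5% of trials at every drift and arm size tried.

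**Baseline-adjusted alternative.** Here both follow-up scores are regressed on baseline and group, each visit having its own baseline slope, with a joint F test of group on 2 and 2n−4 df (n per arm). Power, adjusted versus planned group-by-time (40,000 runs per cell, complete data, effect 0.8 SD):

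| Effect pattern | n per arm | r = 0.5 | r = 0.7 | r = 0.8 |
|---|---|---|---|---|
| Both visits | 15 | 0.73 vs 0.59 | 0.87 vs 0.82 | 0.95 vs 0.95 |
| One visit only | 15 | 0.60 vs 0.59 | 0.80 vs 0.82 | 0.93 vs 0.95 |
| One visit only | 10 | 0.40 vs 0.41 | 0.58 vs 0.62 | 0.75 vs 0.80 |

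Type I error was 0.048–0.052 (planned) and 0.047–0.052 (adjusted). By contrast, if the adjusted difference at each visit is treated as its own test, at least one 95% CI excludes zero in about 9 to 10% of null trials per outcome.

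**Excluding non-finishers.** Suppose 20% of one arm and none of the other are excluded. Let finishing, as a yes/no variable, correlate ρ with the baseline-adjusted outcome. Two equal procedures then differ spuriously by ρ × √(0.2/0.8) × √(1−r²):

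- ρ = 0.3, r = 0.7: 0.3 × 0.5 × 0.714 = 0.11 SD.
- ρ = 0.5, r = 0.5: 0.5 × 0.5 × 0.866 = 0.22 SD.

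**The case against.** The strongest reply is that the right test is already in the plan: the sentence that asks the within-arm question also asks whether changes differ between the groups. The word alone may mean only that each procedure is looked at separately, and the plan states no rule for declaring a procedure effective. On this view the fault is one causal verb, and harm arises only if the report follows it.

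Much of that stands. No test is missing, and a reader who inferred that the trial has no valid comparison would be going beyond the documents. What remains is that the verb is causal under either reading of alone, and that nothing in the plan tells the analyst which of the two answers supports the conclusion.

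A second reply is that the mention of three groups may point to an untreated control. The documents do not support that inference: no third condition is described, and the analysis names two groups. They do not rule it out either, so the remedy depends on the answer.

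A third is that changing the model is not needed to cure a wording fault. That is correct. Baseline adjustment is an efficiency option, with nothing to gain near r = 0.8 and a small loss if the effect is at one visit only. The completer rule and the group count are also separate defects. They matter here because they affect the comparison that would now carry the inference.

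**Conclusion.** The concern holds. With no untreated group described, a within-arm time effect should not be read as an effect of the procedure, and inference should rest on the between-group comparison that is already planned. This should be fixed. It is not fatal, because the valid contrast exists.

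The figure of 19 to 29% assumes 15 per arm, r of 0.5 to 0.7 and 0.3 SD of natural improvement. It is not an estimate of this trial's error rate: with no natural change the rate is 5%, and with more it is higher. The conclusion does not depend on it.

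A reader might also infer that, because the trial is small, a null result could never be compatible with equivalence. The documents do not support that either way, since no margin is given. The defensible statement is narrower: a non-significant difference is not evidence of equivalence, nor that either procedure works. At 15 per arm and r = 0.5, the planned test would miss a true 0.8 SD difference present at both visits in 41% of trials (1 − 0.59).

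**What to change.** 1. **Within-arm aim.** Delete it. Report within-arm changes as means with 95% CIs and draw no efficacy claim from them.
2. **Between-group test.** State that the conclusion for each outcome rests on one test, the planned group-by-time test. Optionally, and only if chosen in advance, replace it with the joint test of group over the two follow-up visits, adjusted for baseline with a separate baseline slope at each visit. Give the difference at each visit with a 95% CI as an estimate, not as a further test.
3. **Non-finishers.** Send them the 1-week and 1-month forms, analyse every randomised participant with follow-up data in the assigned group, and report the number not finishing by arm.
4. **Number of groups.** State how many groups are randomised and what each receives. If there are only two active groups, say that the comparison shows relative efficacy only, and that a non-significant result shows neither that either procedure works nor that they are equivalent. If a third, untreated group exists, describe it and include it in the between-group analysis.

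The cost is revised wording and two online forms for each non-finisher, plus a different SPSS procedure if the optional model is taken. Baseline scores are already collected. The real concession is the claim that each procedure works on its own, which the design as described cannot support.

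### The between-group analysis names no adjustment for the pre-application score, so a group difference at a given follow-up would be estimated less precisely than the collected data allow

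*Combined protocol and SAP*

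**What the plan says.** The only analysis text is the Statistical Analysis section of the combined protocol and SAP. It states: "The repeated measures analysis of variance will be used to see whether EMDR 2.0 Group Application and mhGAP procedures alone resulted in significant changes". By the same method it asks "if there will be a difference in changes between the two groups". No covariate is named. The only other stated use of the starting values is to "compare the pre-application variables of the two groups", by chi-square or t-test.

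The opening text of the protocol says that "a Google Form information comprising data collecting tools will be delivered to the participants who fulfilled the inclusion criteria", and it says so before it describes the random division. The forms are completed again "1 week and 1 month after completing the applications". The number of participants is given as "randomized to be 30 subjects (in three group", whereas the Statistical Analysis section speaks of two groups.

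For reporting, the Statistical Analysis section promises means and SDs for continuous variables, η² as the effect size ("The effect size will be determined using" η²) and a 0.05 significance threshold. It does not mention a confidence interval for the difference between groups.

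**The concern.** A change score carries the random variation of the starting measurement as well as that of the follow-up. Adjusting for the starting measurement removes the part of the follow-up variation that it predicts and does not add its noise back. Both comparisons are valid under randomisation, so what is at stake is precision, not bias.

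Precision is scarce here. Whichever way the figure of 30 is read, the arms are small and any interval for a group difference will be wide. A t-test of the groups at the start is not an adjustment and recovers none of this precision. Because no interval is promised, a reader would see a p value and an η² without learning how large a difference in scale points the data support or exclude.

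**Working it through.** The plan gives no sample-size calculation, SD, effect or correlation, so there is no figure of its own to reproduce.

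**What enters the planned test (inference).** The SAP provides for a correction "In cases where the Mauchly test revealed that the sphericity assumption will be violated". Sphericity is an issue only with three or more time levels. The protocol has two follow-ups, and a change needs a starting value. The pre-application score is therefore very probably the first of three levels, and the between-group test is the group-by-time interaction.

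**Assumed inputs.** Two arms of equal size n; pre-post correlation r of 0.3, 0.5 or 0.7; normal scores; complete forms; first, the same SD σ before and after. The value n = 15 reads the 30 as a total over two arms, and n = 30 reads it as per arm.

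**Variance per person at one follow-up, in units of σ².**
- Change: 2(1 − r)
- Adjusted: 1 − r²
- Ratio: (1 − r²) / [2(1 − r)] = (1 + r)/2

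Estimating the slope multiplies the adjusted variance by 1 + 1/(2n − 4). At n = 15 this is 1 + 1/26 = 1.038, and at n = 30 it is 1 + 1/56 = 1.018.

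| r | (1+r)/2 | n = 15 | n = 30 |
|---|---|---|---|
| 0.3 | 0.65 | 0.65 × 1.038 = 0.68 | 0.65 × 1.018 = 0.66 |
| 0.5 | 0.75 | 0.75 × 1.038 = 0.78 | 0.75 × 1.018 = 0.76 |
| 0.7 | 0.85 | 0.85 × 1.038 = 0.88 | 0.85 × 1.018 = 0.87 |

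**Break-even.** Setting the ratio to 1 gives r = 2/(27/26) − 1 = 0.93 at n = 15 and r = 2/(57/56) − 1 = 0.96 at n = 30.

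**On the interval.** Simulated mean half-width of the 95% confidence interval at 1 month, 15 per arm, in SD units, change versus adjusted: 0.88 v 0.72 at r = 0.3, 0.74 v 0.66 at r = 0.5, and 0.57 v 0.54 at r = 0.7.

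**Unequal SDs.** If the follow-up SD is s times the starting SD, the large-sample ratio is s²(1 − r²)/(1 + s² − 2rs). For r = 0.3, 0.5 and 0.7 it is 0.46, 0.52 and 0.56 at s = 0.75, and 0.78, 0.89 and 0.98 at s = 1.25. In units of the starting variance, the gap between the two variances is (1 + s² − 2rs) − s²(1 − r²) = (1 − rs)², so the gain disappears as rs approaches 1. At s = 1.25, r = 0.7 and 15 per arm, the small-sample cost takes the ratio to 0.98 × 1.038 = 1.02, so nothing is gained there.

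**The case against.** The strongest objection is that the ratios compare adjustment with a one-visit change score, while the plan, as inferred, runs a three-level interaction test on 2 degrees of freedom that uses both follow-ups. That is correct. A reader might infer that the planned test is wrong, or that adjustment would raise the trial's power; the documents support neither. The planned test does address a difference in changes, and the power comparison depends on correlations that the documents do not give.

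Simulation shows no general ordering. With an assumed 0.8 SD effect at both visits, 15 per arm, and correlations of 0.7 (pre to 1 week), 0.7 (pre to 1 month) and 0.85 (between follow-ups), power is 82% for the planned test, 83% for adjusted 1-month scores and 79% for an adjusted joint test of both follow-ups. With correlations of 0.8, 0.7 and 0.9 and two arms of 10, the planned test has 70% and the adjusted 1-month comparison 63%. A single named visit also has only about 5% power if the effect lies entirely at the other visit. Neither adjusted test should therefore be prescribed as a replacement primary test.

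It would also be too strong to say that the plan reports only η² and p values, because it promises means and SDs. What is missing is an interval for the group difference. One could be given for the difference in changes without any adjustment, though in most of the settings above it would be wider.

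Finally, the number of arms is unsettled between the opening text and the Statistical Analysis section. The figures here assume two arms, and the conflict has to be resolved separately.

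**Conclusion.** The point stands as one of precision at a given follow-up. With equal SDs and 15 per arm, the adjusted difference has about 12% to 32% less variance than the difference in change for r between 0.7 and 0.3, and the advantage shrinks to nothing near r = 0.93. It is larger if scores become less variable after treatment, and small or absent if they become more variable and r is high.

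The conclusion rests on assumed correlations and SDs, two equal arms, and the inference that the pre-application score is a time level. It is also an inference, from the order of the opening text, that the form is filled in before allocation. The planned test is not invalidated. Adjustment is worth making because the covariate is apparently already in hand; confidence in how much it matters in this trial is moderate.

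**What to change.** Add to the Statistical Analysis section:

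- For the between-group question, analyse the 1-week and 1-month scores of each scale by analysis of covariance, with group as factor and that scale's pre-application score as covariate.
- Make the adjustment whatever the t-test of the groups at the start shows.
- Report each adjusted group difference in scale points with its 95% confidence interval, beside η².
- State in advance which result the 0.05 threshold applies to, so that the choice between the group-by-time test and the adjusted differences is not made after seeing the data.

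The within-group repeated-measures analysis, the planned group-by-time test and the description of the groups at the start can stay.

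The cost is SAP wording, another procedure in the same package, a little more analysis and one degree of freedom for the slope. The interval would be slightly wider only if the pre-post correlation is very high, or if it is fairly high and scores are more variable at follow-up. No additional data are needed.
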